Firstly, a multi-center trial RCT involving solely ECMO centers would allow for recruitment of sufficient patients for statistical power, and would remove the potential confounding variable of the type of center encountered in the CESAR trial. This would more clearly characterize a survival benefit provided by ECMO itself.

Secondly, the study population will be narrowed to include solely the first definition of respiratory failure employed in the CESAR trial (Murray score >3). The pH <7.2 definition of respiratory failure will be eliminated, as inclusion of patients meeting this parameter who may or may not meet the first parameter potentially diversifies the study group in terms of disease process and pathophysiology to an extent that is difficult to predict. This study will focus on severe ARDS alone as defined by a Murray score >3, with or without hypercapneic respiratory failure.

Hypothesis

For patients with severe but potentially reversible hypoxemic respiratory failure (Murray score >3) secondary to ARDS admitted to a center with ECMO, ECMO will increase survival without severe disability at 6 months post-randomization by a proportion of 25% as compared to non-ECMO ICU management at these same centers (including vent management by a pulmonologist as well as ARDSnet protocol).

Methods

a. Conceptual and Operational Definitions:

Study outcome will be a composite outcome of survival without severe disability at 6 months. Severe disability will be defined as being bed-bound and unable to wash and dress oneself.

b. Study Design

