The study will be a longitudinal, prospective, un-blinded, parallel-arm, multi-center, intention to treat, RCT, composed of centers with adult ECMO experience. Study subjects will include patients aged 18-65 admitted to these centers who are diagnosed with potentially reversible hypoxemic respiratory failure. Upon diagnosis with ARDS at the ECMO center, the components of the Murray score will be monitored every 2 hours. Once a Murray score >2.5 is obtained, the intensive care team will begin to profile the patient for the study and contact a study representative if the patient's consenting family member is willing to speak with them (the consenting family member will provide initial consent, then, once able the patient can choose whether or not to continue with the trial). Data collection for all study members will include demographics, diagnosis leading to ARDS, dates of hospitalization/ intubation/ extubation, dates of transfers/discharges, conditions at discharge, complications, cause of death, vent settings, blood gases, hemodynamic status, APACHE II, Murray lung score. Once a Murray score of 3.0 is obtained, the study subject will be randomized to conventional therapy or to ECMO. Given the large potential for other variables to significantly affect the primary outcome of mortality, randomization will be stratified in a fashion similar to that done in the CESAR trial. Stratification will be performed for age, hours of high P/high FiO₂, and number of organs failed (see Appendix 2).

Conventional therapy will include ARDSnet protocol vent management strategy with vent strategies guided by a pulmonologist. Data collection for the conventional management group will include time course, complications, and success with fulfillment of ARDSnet protocol (low-

volume, low-pressure with $P_{plat} < 30$). For the ECMO group, V-V ECMO with percutaneous cannulation will be used, with standardized lung rest vent settings (P_{pk} 20-25, P_{pl} 10-15, rate 10, FiO_2 30%), and ECMO will be continued until lung recovery is deemed obtained or until apparent irreversible multi-organ failure is attained. Data collection for the ECMO group will include cannulation information, flow, sweep, and pressure rates, and complications information.

c. Statistical Analysis:

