The estimated mortality for severe ARDS is 70% (NIH ARDS network database). As with the CESAR trial, an estimate of 10% severe disability in both trial arms will be used. For sample size calculation, Alpha will be set at 0.05 and Beta at 0.2. An effect size of a 25% proportional disability free survival benefit (70% mortality \rightarrow 52.5 mortality, or 17% difference in mortality) is estimated, which mirrors the effect size observed in the CESAR trial; using chi square testing this equates to a n of 132 patients for each study group.

C. Study procedures:

Intubation

All patients in this study will have respiratory failure prior to randomization, such that intubation and mechanical ventilation will occur prior to the study.

ECMO placement and maintenance

V-V ECMO will be placed for all patients randomized to the ECMO group. This requires a surgeon placing large catheters into the neck, in to the internal jugular vein, through a small incision. This is a simple, brief surgical procedure requiring sedation and anesthesia. Once the ECMO catheter has been placed, sedation will be used in order to prevent the patient from awakening and removing or moving the ECMO catheter, which is sutured in place in the neck. The catheters placed in the neck will extract blood from the heart that will then be run through the ECMO circuit for the purpose of oxygenating the blood and removing carbon dioxide from the blood. The ECMO circuits consist of pumps, membrane oxygenators, and filters. Blood running through the ECMO circuit has an increased risk of clotting such that all patients put on ECMO will receive heparin in order to avoid clotting. The heparin used to avoid clotting creates an increased risk of bleeding. To ensure that the therapeutic effect of heparin is appropriate, coagulation studies will be performed using simple blood tests.

D. Study Drugs: N/A

E. Medical Devices:

ECMO device

The ECMO circuit includes a Stockert SIII servo-controlled roller pump, Medtronic tubing, Medtronic .8meter squared membrane oxygenator, Medtronic ECMOTherm heat exchanger, a Stockert SIII control desk with dual pressure monitors, and Transonics Systems HT110 bypass

flow meter. Stockert—Freiburg, Germany; Medtronic—Minneapolis, MN; Transonics—Ithaca, NY.

Ventilator

Puritan Bennett 840 ventilators will be used.

F. Study Questionnaires:

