Appendix 2: Stratification guidelines

- a) Age (18-30, 31-45, 46-65)
- b) Hours of high P / high FiO₂ ventilation (0-48, 49-168)
- c) Number of organs failed (1-2 vs 3 or more); failure defined using SOFA score ≥ 2
 - i. Resp—p/f: $<400=1$, $<300=2$, $<200+\text{vent}=3$, $<100+\text{vent}=4$
 - ii. CNS—GCS: $13-14=1$, $10-12=2$, $6-9=3$, $<6=4$
 - iii. CV—MAP: $<70=1$, $\text{DA}=2$, $\text{DA}>5 / \text{epi}<=0.1 / \text{NE } <=0.1 = 3$, $\text{DA}>15 / \text{epi}>0.1 / \text{NE } >0.1 = 4$
 - iv. Liver—Bili: $1.2-1.9=1$, $2-5.9=2$, $6-11.9=3$, $>12=4$
 - v. Coagulation—Plts: $<150=1$, $<100=2$, $<50=3$, $<20=4$
 - vi. Renal—CRE: $1.2-1.9=1$, $2-3.4=2$, $3.5-4.9$ or uop $<500=3$, <5 or UOP $<200=4$

References

1. Morris et al. Randomized Clinical Trial of Pressure-controlled Inverse Ratio Ventilation and Extracorporeal CO₂ Removal for Adult Respiratory Distress Syndrome. *American Journal of Respiratory and Critical Care Medicine*. Vol 149, No 2. Feb 1994, 295-305.
2. Peek et al. Efficacy and Economic Assessment of Conventional Ventilatory Support Versus Extracorporeal Membrane Oxygenation for Severe Adult Respiratory Failure (CESAR): a Multicentre Randomized Controlled Trial. *The Lancet*. Vol 374. Oct 17, 2009.
3. Peek et al. CESAR Study Protocol. *BMC Health Services Research*. 6:163. Dec 23, 2006.
4. UK Collaborative ECMO Group. The Collaborative UK ECMO Trial: Follow-up to 1 Year of Age. *Pediatrics*. Vol 101. No 4. April 1998.
5. Zaponi et al. Extracorporeal Membrane Oxygenation in Severe Acute Respiratory Failure: A Randomized Prospective Study. *JAMA*. Vol 242. No 20. Nov 16, 1979.

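### Randomisation is stratified on three patient factors but not on centre, so each centre's split between arms is left to chance

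*Protocol*

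**What the plan says.** Section B, Methods b (Study Design) describes the trial as "un-blinded, parallel-arm, multi-center, intention to treat, RCT, composed of centers with adult ECMO experience". It gives a reason for stratifying: "Given the large potential for other variables to significantly affect the primary outcome of mortality, randomization will be stratified". It then names the factors: "Stratification will be performed for age, hours of high P/high FiO₂, and number of organs failed (see Appendix 2".

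Appendix 2 sets the levels:
- "Age (18-30, 31-45, 46-65": three levels
- "Hours of high P / high FiO₂ ventilation (0-48, 49-168": two levels
- "Number of organs failed (1-2 vs 3 or more": two levels

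Centre appears in neither list. The protocol mentions no lists held by site, no blocking within centre and no minimisation. The number of centres is not given. Section B, Methods c plans 132 patients per group and names only a chi-square test.

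On centres, the opening of section B says that using only ECMO centres "would remove the potential confounding variable of the type of center encountered in the CESAR trial".

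**The concern.** Stratifying on patient factors balances the arms within those factors, not within a hospital. Care in both arms depends on local staff. For the ECMO arm, section C states: "This requires a surgeon placing large catheters into the neck". In the control arm a pulmonologist at the site directs ventilation. Centres may therefore differ in outcome. That is an inference from how care is delivered, since the protocol gives no data on variation between centres.

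If outcomes do differ, a centre with high or low mortality that happens to split unevenly adds noise to the treatment comparison. A centre with very uneven arms also says little about whether the effect is consistent across sites. The choice has to be settled before the first patient is randomised: a later analysis plan can adjust for centre but cannot restore balance within it.

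**Working it through.** **Inputs from the protocol.** 70% v 52.5% mortality, alpha 0.05, power 80%, 132 per group, so N = 264 (section B, Methods c). Factor levels are from Appendix 2.

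**Assumptions.** The number of centres k (3 to 20), near-equal centre sizes, and a between-centre SD of 0.5 to 1.0 on the log-odds scale. None of these is in the protocol.

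**1. The plan's own figure.** The mean proportion is (0.70 + 0.525)/2 = 0.6125. The two-sided formula is

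n = [1.960·√(2 × 0.6125 × 0.3875) + 0.842·√(0.70 × 0.30 + 0.525 × 0.475)]² / 0.175² = 120.5.

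The continuity correction gives (120.5/4)·[1 + √(1 + 4/(120.5 × 0.175))]² = 131.7, so 132. The stated size is reproduced.

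**2. Chance of an uneven centre.** In a centre of m patients with no balancing by centre, take the ECMO count X as Binomial(m, ½). Let p(m) = P(max(X, m − X) ≥ 2m/3). The chance that at least one centre is split 2:1 or worse is 1 − Π(1 − p(m)) over the centres. Treating centres as independent is an approximation.

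| Centres | Sizes (sum 264) | p(m) | At least one 2:1 or worse |
|---|---|---|---|
| 3 | 3 × 88 | 0.0018 | 0.5% |
| 5 | 4 × 53, 1 × 52 | 0.0127, 0.0175 | 7% |
| 10 | 6 × 26, 4 × 27 | 0.0755, 0.1221 | 63% |
| 15 | 9 × 18, 6 × 17 | 0.2379, 0.1435 | 97% |

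For 10 centres, for example: 1 − 0.9245⁶ × 0.8779⁴ = 0.63. These values move noticeably with a single patient more or fewer per centre, so they show an order of size only.

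**3. What balancing by centre would change.** Permuted blocks of 4 within the 12 patient strata were simulated against permuted blocks of 4 within centre. The median worst centre split falls from about 59:41 to 51:49 (5 centres), from 67:33 to 53:47 (10) and from 80:20 to 60:40 (20).

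**4. Effect on the treatment estimate.** Write n₁ⱼ and n₀ⱼ for the two arm counts in centre j, and πⱼ for its mortality. Chance imbalance alone shifts the difference by Σ(n₁ⱼ − n₀ⱼ)πⱼ/132. This was simulated with 132 v 132 randomised without regard to centre, 70% mortality and 5 to 15 centres:
- mean shift: 0;
- SD: about 1.1 to 1.2 percentage points for a log-odds SD of 0.5, and 2.1 to 2.3 for 1.0;
- 95th percentile of the absolute shift: about 2.3 to 4.5 points.

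For comparison, the planned difference is 17.5 points, and the sampling SD at 70% in both arms is √(2 × 0.70 × 0.30/132) = 5.6 points.

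In the simulation of step 3, run under no treatment effect, the unadjusted test rejected in about 3% to 6% of runs. The SD of the estimated difference was about 0.055 to 0.059 with patient strata only and 0.053 to 0.056 with centre blocks.

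**5. Whether centre can simply be crossed in.** 3 × 2 × 2 = 12 strata, and 264/12 = 22 patients each. Crossing with 5, 10 or 20 centres gives 60, 120 or 240 cells, averaging 4.4, 2.2 or 1.1 patients.

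**The case against.** A reader might infer that the protocol defeats its own purpose: it sets out to take the centre out of the comparison and then lets centre back in. The text does not support that. The claim in section B concerns the type of centre. In the earlier trial, ECMO was tied to referral to an ECMO centre, so arm and type of centre went together systematically. Randomising patients inside ECMO centres, with controls managed at the same centres, does remove that. What remains is chance imbalance with mean zero, which the standard error of a randomised comparison covers. Calling it confounding would overstate it. This part of the objection stands in full.

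It is also fair that a 2:1 split in one small centre barely moves a 264-patient result, and that the probability of such a split runs from negligible to near certain on the assumed number of centres alone. The protocol limits variation too: ARDSnet ventilation, standardised lung-rest settings and named equipment. Adjusting for centre, which the analysis plan (not seen here) may provide for, would recover most of the small loss of precision.

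Two arguments carry less weight. Lists held separately at each site would stratify by centre in practice, but the protocol does not say this and gives a closed list of three factors. The protocol also likens its scheme to that of the earlier trial, but how that trial handled centre cannot be checked from this document. Finally, small blocks within centre would make assignments easier to guess in an un-blinded trial. That bears on how centre is added, not on whether it should be.

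**Conclusion.** The point holds as a worthwhile, low-cost improvement to the design. Centre is missing from a stated, closed list of randomisation factors in a multi-centre trial with locally delivered care.

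The cost is some precision and weaker interpretation by site. It is slight with a handful of large centres and grows with many small ones. Under the assumed variation between centres, the added SD of about 1 to 2 percentage points is small beside the sampling SD of 5.6 points and the planned difference of 17.5. The figures rest on an unstated number of centres, near-equal sizes and an assumed between-centre SD.

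The documents do not support reading this as bias, as a materially inflated type I error, or as a contradiction of the protocol's rationale.

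**What to change.** Before enrolment, add centre to the randomisation factors in section B, Methods b and in Appendix 2. Use central minimisation with a random element over centre, age band, hours band and organ count. Full crossing is not workable, since it would leave about 4 or fewer patients per cell with 5 or more centres. Adjust the primary analysis for the randomisation factors, handling centre in a way that tolerates small sites.

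The cost is an amended sentence, an added line in Appendix 2 and a revised randomisation specification. A central algorithm is needed, and slight predictability remains, which the random element limits. The sample size stays at 132 per group.

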[name], PGY-1

Columbia Presbyterian Internal Medicine Program

CRC IRB Protocol, December 2010

Conventional Ventilatory Support versus Extracorporeal Membrane Oxygenation for Severe ARDS: a Trial within Multiple ECMO Centers

A. Study Purpose and Rationale

ECMO (extracorporeal membrane oxygenation) is a technology used in ICU settings to provide cardiopulmonary bypass that enables reduction of ventilatory settings while avoiding severe hypoxemia and hypercapnea; the potential harm of positive pressure ventilation in the forms of baro-trauma, volu-trauma and oxygen toxicity can potentially be avoided through this technology. Originally developed in the 1970s, ECMO has seen significant device improvements that may expand its future indications. At present, it is well proven in respiratory failure in neonates however its role in treating adults remains under question. A randomized controlled trial that definitively shows mortality benefit of ECMO as compared to standard intensive care therapy for adult patients with respiratory failure remains necessary.

Review of the Literature

RCTs in neonates provide convincing evidence for the use of ECMO, with a number needed to treat between three and four infants for a mortality benefit at 1 year⁴. In adults, three prior RCTs exist, two of which are dated studies that showed no benefit^{1,5}. The most recent RCT was the CESAR trial, in which adults in the UK with respiratory failure defined as a Murray Score >3 (see appendix 1) or pH <7.2 were randomized either to conventional therapy or to referral to one ECMO center. This trial showed a disability free survival benefit for ECMO center referral (63% mortality for standard therapy vs 47% in ECMO center referral group, p=0.03) (disability defined as severe disability—bedbound and unable to wash/dress self). Within the group randomized to referral to the ECMO center, only 75% of these patients ultimately received ECMO. Overall the study was limited in its ability to make conclusions regarding the benefit of ECMO itself rather than referral to an ECMO center. A RCT that investigates the mortality benefit of ECMO itself would provide more appropriate justification for the role of ECMO in adults with respiratory failure.

B. Study Design and Statistical Procedures

The proposed trial will be modeled largely after the recent CESAR trial with several important differences.

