For the purpose of identifying the primary endpoint, a brief questionnaire will be completed via phone interview asking after the disability status of the patients 6 months after randomization. Two simple yes/no questions will be answered: is the patient bedbound? Is the patient able to dress and wash his/her self?

G. Study Subjects:

Patients for this study will include patients admitted by any means (either transferred patients or patients entering the hospital via the ED of the ECMO center hospitals) to the ECMO centers involved in the study. In all cases, ECMO will be initiated following randomization at the ECMO study center.

Inclusion criteria will include adult patients (18-65 yo) with severe but potentially reversible hypoxemic respiratory failure despite optimal conventional treatment at the same study centers providing ECMO. Respiratory failure as mentioned will be defined by Murray score >3.0

Exclusion criteria will include duration of high P (>30 cm Ppk) and/or high FiO₂ (>0.8) ventilation for >7 days, intra-cranial bleeding or any other absolute contraindications to heparinization, hypoxemic respiratory failure not fulfilling ARDS definition or hypoxemic respiratory failure deemed irreversible by a study consultant, moribund patients deemed to have minimal chance for survival regardless of chosen intervention as defined by a study consultant. ARDS related hypoxemic respiratory failure implies acute onset of a potentially reversible pathophysiology for which 'lung rest' allowing for low pressure/low FiO₂ vent settings may provide mortality benefit through avoidance of baro/volu-trauma and oxygen toxicity as well as avoidance of any degree of hypoxemia during the acute phase of disease; this is the rationale for excluding nonreversible and chronic hypoxemic respiratory failure.

H. Recruitment of Subjects:

As mentioned above, study subjects will be identified by ARDS diagnosis and by Murray score. Once an ARDS diagnosis is made, Murray score parameters will be monitored every 2 hours, and once Murray score is >2.5 , the patient's primary intensivist will then ask after the consenting family member as to the willingness to speak with a study representative.

I. Confidentiality of Study Data

A unique code will be created for each study participant for identification purposes and for data collection. Data will be secured in a secure location, only accessible by investigators.

J. Potential Conflict of Interest: Unknown.

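### The sample size of 132 per arm reproduces from mortality alone, so 80% is not shown to be the power for the primary endpoint of survival without severe disability

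*Protocol*

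**What the plan says.** Protocol section B, Methods a (Conceptual and Operational Definitions): "Study outcome will be a composite outcome of survival without severe disability at 6 months". The Hypothesis in section B uses the same endpoint and puts the effect on its scale: "ECMO will increase survival without severe disability at 6 months post-randomization by a proportion of 25" percent. Section F (Study Questionnaires) also ties the primary endpoint to disability: "For the purpose of identifying the primary endpoint, a brief questionnaire will be completed via phone interview asking after the disability status".

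Section B, Methods c (Statistical Analysis) takes a control mortality of 70% and adds: "As with the CESAR trial, an estimate of 10% severe disability in both trial arms will be used". It sets the error rates ("Alpha will be set at 0.05 and Beta at 0.2") and names the effect as a 25% proportional benefit in disability-free survival. It expresses that effect only as mortality falling from 70% to 52.5%, and derives 132 patients per group by chi-square testing.

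One clause, in section B, Methods b (Study Design), names a different outcome when it justifies stratification: "Given the large potential for other variables to significantly affect the primary outcome of mortality".

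**The concern.** Methods c labels the effect with the composite but gives it numerically as mortality. It announces a disability rate and then shows no calculation that contains it. If 132 comes from mortality alone, the trial's one stated power figure describes a comparison other than its primary one.

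The 25% also appears on two scales. The Hypothesis describes a proportional rise in a good outcome. Methods c applies a proportional fall to a bad outcome. When the bad outcome is common these differ greatly: mortality falling from 70% to 52.5% is a 25% relative fall in death, but a 17.5/30 = 58% relative rise in survival (30% to 47.5%).

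At stake is whether those who approve the trial know what difference in disability-free survival 132 per arm can detect.

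**Working it through.** **Inputs.** From Methods c: control mortality 70%, ECMO mortality 52.5% (0.70 × 0.75), severe disability 10% in both arms, alpha 0.05, beta 0.2, chi-square test, 132 per group. Not stated, so assumed: two-sided alpha and a continuity correction (both inferred from the exact match in step 1), and no loss to follow-up.

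**Formulas**, with p̄ = (p1 + p2)/2 and d = |p1 − p2|:

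- Uncorrected: n = [1.960·√(2p̄(1−p̄)) + 0.8416·√(p1(1−p1) + p2(1−p2))]² / d²
- Continuity-corrected: n_c = (n/4)·[1 + √(1 + 4/(n·d))]²

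**Step 1: reproduce the plan's figure.** For 70% v 52.5%, p̄ = 0.6125 and d = 0.175.

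- n = (1.960 × 0.6890 + 0.8416 × 0.6778)² / 0.175² = (1.3504 + 0.5704)² / 0.030625 = 120.5
- n_c = (120.5/4)·[1 + √(1 + 4/(120.5 × 0.175))]² = 131.7, so **132**, an exact match.

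Other variants of the mortality contrast miss: uncorrected 121; one-sided 95 (106 corrected); 70% v 53%, using the rounded 17-point difference, 128 (139 corrected). The 10% plays no part in the match.

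**Step 2: build the composite (failure = death or severe disability).** The denominator of the 10% is not stated, so both are shown.

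- 10% of all randomised, added to each arm: 70 + 10 = 80%; 52.5 + 10 = 62.5%.
- 10% of survivors: 70 + 0.10 × 30 = 73%; 52.5 + 0.10 × 47.5 = 57.25%.

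Neither pair is a 25% relative fall in the composite: 17.5/80 = 21.9% and 15.75/73 = 21.6%. Taking 25% off the composite itself gives 80 × 0.75 = 60% and 73 × 0.75 = 54.75%.

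The Hypothesis read literally, on the all-randomised denominator, is disability-free survival rising from 20% to 20 × 1.25 = 25%.

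**Step 3: size and power.** The n columns give the size for 80% power. Power at 132 per arm is by exact enumeration of the chi-square test. Continuity-corrected values are in brackets.

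| Contrast | Reading | n per arm | Power at 132 |
|---|---|---|---|
| 70% v 52.5% | mortality alone | 121 (132) | 84% (80%) |
| 80% v 62.5% | 10% of all randomised | 104 (115) | 89% (86%) |
| 80% v 60% | 25% off that composite | 82 (91) | 95% (93%) |
| 73% v 57.25% | 10% of survivors | 143 (155) | 77% (73%) |
| 73% v 54.75% | 25% off that composite | 108 (119) | 87% (84%) |
| 20% to 25% disability-free | Hypothesis read literally | 1094 (1134) | 16% (13%) |

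No composite pair built with the 10% returns 132.

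**The case against.** The best defence is that the protocol uses mortality loosely for the composite. Its literature review reports CESAR's disability-free survival benefit as "63% mortality for standard therapy vs 47% in ECMO center referral group", and Methods c follows the same pattern. If 70% and 52.5% are shorthand for death or severe disability, then 132 and 80% do belong to the primary endpoint. This cannot be excluded. It fits poorly, though: Methods c introduces 70% as the mortality of severe ARDS and then adds the 10% as a separate estimate to be used, which on this reading would have no function. The ambiguity itself still needs resolving.

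A second defence is that an equal 10% in both arms cancels. It cancels from the difference only if it is 10% of all randomised. Even then the variance changes and the corrected size falls from 132 to 115. On the survivor denominator the difference itself shrinks from 17.5 to 15.75 points.

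Three stronger claims are tempting, and the document does not support them:

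- **That CESAR's rates should give 132.** Methods c says its effect size mirrors CESAR's, not its event rates. 47/63 = 0.746 is a 25% relative reduction, so the statement is broadly consistent.
- **That the protocol names two primary endpoints and leaves room to choose between them later.** The Hypothesis, the definitions and section F all use disability status. The exception is one clause about stratification, best treated as a wording slip.
- **That the trial is underpowered.** Of the four readings based on a reduction in failures, three give more than 80% power and only 73% v 57.25% falls below.

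**Conclusion.** The point holds as a mismatch between endpoint and calculation. The 132 per arm is the mortality size to the patient, the stated 10% does not enter, and 80% is not shown to be the power of the primary analysis.

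The direction is open. Across the four readings based on failure reduction, power at 132 runs from 73% to 95%. The Hypothesis taken literally gives 13% to 16%. For that reason a reader should infer neither that the trial is underpowered nor that restating the power will change it only slightly: either could be wrong until the rates and the scale of the effect are fixed.

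The conclusion assumes a two-sided test and no dropout. The continuity correction is inferred from the match, and both forms are shown because they do not alter the finding.

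**What to change.** In section B, Methods c:

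1. State the assumed rate of death or severe disability at 6 months in each arm.
2. Say whether the 10% is of all randomised patients or of survivors.
3. Say whether the 25% is a relative fall in death or disability or a relative rise in disability-free survival, and word the Hypothesis to match.
4. State the sidedness and whether a continuity correction is applied, then restate the power that 132 per arm gives for that contrast.

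In Methods b, replace the reference to mortality as the primary outcome with the composite.

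The cost is protocol wording and one recalculation. Whether 132 per arm remains adequate can be judged only after items 1 to 3 are settled, so the number should be neither confirmed nor changed before then.

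### Randomisation is stratified on three factors, but the only test named is a plain chi-square, which would be mildly conservative if it is also the primary test

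*Protocol*

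**What the plan says.** Protocol section B, Methods, b. Study Design gives the reason for stratifying: "Given the large potential for other variables to significantly affect the primary outcome of mortality, randomization will be stratified". The factors are age, hours of high-pressure/high-oxygen ventilation and number of failed organs. Appendix 2 sets the levels: three age bands, two bands of hours, and for the third factor "Number of organs failed (1-2 vs 3 or more); failure defined using SOFA score" (threshold 2). That makes 3 × 2 × 2 = 12 strata.

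Section B, Methods, c. Statistical Analysis contains only the sample-size calculation. It states "Alpha will be set at 0.05 and Beta at 0.2", a fall from 70% to "52.5 mortality, or 17% difference in mortality", and then "using chi square testing this equates to a n of 132 patients for each study group". Chi-square is the only test named in the protocol. No stratified or covariate-adjusted method is mentioned, and the analysis is not referred to another document.

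**The concern.** Stratified randomisation balances the arms on the chosen factors, so outcome differences between strata largely drop out of the treatment contrast. A plain two-group chi-square does not know this: its variance still contains the between-stratum part. Its standard error is then larger than the real sampling variation, the confidence interval is too wide, and the test rejects less often than its nominal 5% under the null.

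The reason given for stratifying and the only test named therefore do not match. At stake is some efficiency: a stratified test on the same 264 patients would have somewhat more power and an interval of the right width. The better the factors predict the outcome, which is the protocol's own premise, the larger the gap.

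**Working it through.** **1. The plan's own figure.** Inputs from c. Statistical Analysis: p₁ = 0.70; p₂ = 0.70 × 0.75 = 0.525; difference d = 0.175; alpha 0.05, taken as two-sided because that reproduces the stated n; power 0.80. Mean rate p̄ = 0.6125.

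- Uncorrected: n = [1.960·√(2 × 0.6125 × 0.3875) + 0.842·√(0.70 × 0.30 + 0.525 × 0.475)]² / 0.175² = (1.3504 + 0.5704)² / 0.030625 = 120.5, so 121 per group.
- With continuity correction: n′ = (n/4)·[1 + √(1 + 4/(n·d))]² = 30.12 × (1 + √1.1897)² = 131.7, so **132 per group**, as stated.
- Power of the uncorrected test at 132 per group: Φ[(0.175 × √132 − 1.3504)/0.6778] = Φ(0.974) = 83.5%.

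**2. Why ignoring strata widens the error.** Under the null, let stratum s have event rate pₛ, with overall rate p. The average within-stratum variance is p(1 − p) − Var(pₛ). The plain chi-square uses p(1 − p). With balance within strata its standard error is therefore too large by about √{p(1 − p) / [p(1 − p) − Var(pₛ)]}. The excess is zero if the strata do not differ and grows as they do.

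**3. Size, by simulation.** The protocol gives no stratum mix and no stratum event rates, so both are assumptions. Setup: 264 patients, 12 strata, allocation balanced within strata, overall rates 70% and 52.5% (70% in both arms under the null), two-sided 0.05. There were 20,000 trials for power and 40,000 for type I error. The CMH statistic is Σ(x₁ₛ − n₁ₛmₛ/Nₛ) / √Σ[n₁ₛn₀ₛmₛ(Nₛ − mₛ)/(Nₛ²(Nₛ − 1))], where in stratum s x₁ₛ is the events in the ECMO arm, mₛ the total events, n₁ₛ and n₀ₛ the arm sizes, and Nₛ the stratum size.

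Assumed mix: age 25/35/40%, hours 65/35%, organs 50/50%. Both tests are without continuity correction.

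| Assumed odds ratios (per age band; hours; organs) | Power, chi-square | Power, CMH | Gap (points) | Type I error, chi-square |
|---|---|---|---|---|
| Moderate (1.5; 1.5; 2) | 84.7% | 85.7% | 1.0 | 4.4% |
| Strong (1.8; 2; 3) | 85.0% | 87.7% | 2.7 | 3.8% |
| Very strong (2; 2; 4) | 85.5% | 88.9% | 3.4 | 3.4% |

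The type I error of CMH is about 5% throughout.

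A second set of assumptions (age 25/30/45%, hours 60/40%, organs 60/40%; the same odds ratio from lowest to highest level of each factor) shows the range:

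| Odds ratio | Power, chi-square | Power, CMH | Type I error, chi-square | Excess of ordinary SE |
|---|---|---|---|---|
| 1.0 | 84.1% | 83.9% | 5.0% | none |
| 1.65 | 83.7% | 84.2% | 4.7% | about 1% |
| 2.7 | 85.2% | 87.8% | 4.0% | about 6% |
| 4.5 | 86.6% | 91.4% | 2.9% | about 12% |

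**4. Continuity correction.** The stated n follows only from the corrected chi-square. If that version were also the one applied, its power in the three scenarios of the first table would be 81.2%, 81.7% and 82.1%, and its type I error 3.1%, 2.6% and 2.4%. About 3.3 to 3.5 points of its shortfall against CMH then come from the correction (84.7 − 81.2, 85.0 − 81.7, 85.5 − 82.1), not from ignoring the strata.

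**5. Stratum size.** 264/12 = 22 patients on average, or 11 per arm. Under the first assumed mix the smallest stratum expects 264 × 0.25 × 0.35 × 0.50 = 11.6 patients.

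**The case against.** The strongest objection is that chi-square appears only as the way n was set. No sentence says that the outcome will be tested by it, that the test will be unstratified, or that adjustment is excluded. A plain two-proportion test is a usual and cautious basis for planning, and the adjusted model is often left to a statistical analysis plan, which is not shown here. This stands: a reader might infer that the protocol fixes an unstratified primary test, and it does not. What remains is that chi-square is the only test under the analysis heading and no other document is pointed to, so someone following this protocol alone would use it.

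The size of the loss is also assumed. The protocol does not call the factors strongly prognostic; it speaks of their large potential to matter and gives no rates by stratum. The simulations assume balance in all 12 strata, while the protocol states no block or minimisation scheme. Looser balance would reduce the conservatism.

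Nor is the precision gained by stratifying wasted altogether. Balance reduces the true variance whichever test is used, and the chi-square's own power rises from 84.7% to 85.5% across the first table. Only the reported standard error fails to follow.

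**Conclusion.** The point holds as a minor matter of efficiency and clarity, conditional on the named test also serving as the primary one. The plain chi-square would then be mildly conservative: type I error about 4.4% to 3.4%, and power about 1 to 3 points below CMH, for assumed moderate to very strong prognosis. More extreme assumptions give about 5 points, and weak factors give none.

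Two stronger readings are not supported. A reader might infer that the trial is underpowered or that n is wrong. In fact the uncorrected chi-square has about 84% to 87% power over the range in the second table, and the corrected one 80% to 83%, so the planned 80% is kept. A reader might also infer that a positive result would be unsafe. The error is on the cautious side, and type I error is not inflated.

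**What to change.** Add one sentence to c. Statistical Analysis, or a reference there to the statistical analysis plan that contains it: the primary comparison accounts for the three stratification factors. Either form will do:

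- a Cochran-Mantel-Haenszel test over the randomisation strata, with a stratified risk difference and 95% CI; or
- logistic regression with the three factors as main effects, reported as a standardised risk difference with 95% CI. This spends 2 + 1 + 1 = 4 terms on the factors, against 11 for the full set of strata.

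State before outcome data are examined how sparse strata will be handled, for example a fixed order in which levels are merged. A random centre effect is not part of this fix: centre is not a stratification factor, and the number of centres is not given. Keep the plain chi-square as the sizing method and as a sensitivity analysis, and keep "a n of 132 patients for each study group".

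The cost is wording only. The three factors must be recorded to randomise, and no patients or data are added.
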